#### 6.2.1.1 Adverse Events of Interest (AEI) and Other Important AEs

Summaries for treatment-emergent AEIs events will be provided by PT for each AEI category:

- Skin-related events
- Infection events
- Malignancy events

Creatine kinase (CK) elevation for CK elevation  $> 2.5$  upper limit of normal will be summarized as CTCAE grade 2 or higher in the clinical laboratory summaries.

Additional information collected for some events as part of the clinical safety program and adjudicated events will also be summarized.

#### 6.2.1.2 Serious Adverse Events

Summaries for treatment-emergent SAEs will be provided for the following:

- Treatment-emergent SAEs by SOC and PT

#### 6.2.1.3 Adverse Events Leading to Discontinuation of Study Treatment or Study Treatment Interruption

Summaries for TEAEs leading to discontinuation of study treatment will be provided for the following:

- TEAEs by SOC and PT

Summaries for TEAEs leading to study treatment interruption will be provided for the following:

- TEAEs by SOC and PT

#### 6.2.2 Deaths

All adverse events with an outcome of death will be listed.

#### 6.2.3 Clinical Laboratory Data

Laboratory parameters will be summarized using the International System (SI) of Units and US conventional units. Data will be summarized by time point, as applicable. The following summaries will be provided for each parameter:

- Absolute and change from baseline values for continuous parameters

Sponsor: Bristol-Myers Squibb

Protocol no: IM011046

- Number and percentage of subjects for the following:
  - Maximum postbaseline CTCAE grade for each applicable laboratory parameter through Week 16
  - Shifts from baseline based on maximum postbaseline CTCAE grade through Week 16
- Drug-induced Liver Injury (DILI) and Hy's Law summaries

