### **9.5 Safety Analyses**

Safety data will be analyzed for AEs, SAEs, laboratory analytes, vital signs, ECGs, and suicidality and depression. Safety will be summarized using the As-treated population. Categorical data will be summarized as frequency counts and percentages. Continuous data will be summarized using n, mean, standard deviation, median, minimum, and maximum unless otherwise specified.

During the first 16 weeks of treatment, data will be presented for the following treatments:

- BMS-986165 6 mg QD
- Apremilast 30 mg BID
- Placebo

After Week 16, data will be presented for the following treatments:

- BMS-986165 6 mg QD
- Apremilast 30 mg BID
- Placebo to BMS-986165 6 mg QD (starting from Week 16 through Week 52)
- All BMS-986165 6 mg QD (all subjects exposed to BMS-986165 6 mg QD; includes subjects on placebo that switched to BMS-986165 6 mg QD)

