## 4.2 Safety

The safety outcomes include the following:

- Adverse events (AEs)
  - Treatment-emergent adverse events (TEAEs) – defined as:
    - AEs which occur after the first dose of study treatment through 30 days after the final dose of the study treatment or subject's participation in the study if the last scheduled visit occurs at a later time.
  - Treatment-emergent adverse events of interest (AEIs) for the following events:
    - Skin-related AEs
    - Infection AEs, including influenza
    - Creatine kinase (CK) elevation (evaluated as lab toxicity grade 2 or higher)
    - Malignancy
  - SAEs
  - Deaths
- Clinical laboratory parameters
  - Absolute and change from baseline values
  - Laboratory abnormalities (as determined by Controlled Terminology Criteria for Adverse Events [CTCAE v5.0] grading) presented as the worst postbaseline toxicity group
  - Shifts from baseline to maximum postbaseline value
  - Potential drug induced liver injury (DILI) is defined as a subject who meets the following criteria:
    - 1) ALT or AST elevation >3 times ULN  
AND  
▪ 2) Total bilirubin >2 times ULN, without initial findings of cholestasis (elevated serum alkaline phosphatase)  
AND  
▪ 3) No other immediately apparent possible causes of liver function test elevation and hyperbilirubinemia, including, but not limited to, viral hepatitis, preexisting chronic or acute liver disease, or the administration of other drug(s) known to be hepatotoxic.
    - ALT or AST elevation >5 times ULN
- Vital signs
  - Absolute and change from baseline values
  - Marked abnormalities defined by the below categories:
    - Heart rate:
      - Value > 100 and change from baseline > 30
      - Value < 55 and change from baseline < -15
    - Systolic blood pressure:
      - Value > 140 and change from baseline > 20

Sponsor: Bristol-Myers Squibb

Protocol no: IM011046

- Value < 90 and change from baseline < -20
- Diastolic blood pressure:
  - Value > 90 and change from baseline > 10
  - Value < 55 and change from baseline < -10
- Electrocardiograms (ECGs)
  - Absolute and change from baseline values
  - Marked abnormalities defined by the below categories:
    - QT interval corrected using Fridericia's formula (QTcF):
      - 450 -< 480 msec
      - 480 -< 500 msec
      - $\geq$  500 msec
      - $30 < \text{change from baseline} \leq 60$  msec
      - Change from baseline > 60 msec
      - Males: < 450 msec,  $\geq$  450 msec
      - Females: < 470 msec,  $\geq$  470 msec

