## 6.0 Statistical Analyses

Descriptive summaries and analyses will be presented for data captured throughout the study using the following treatment groups.

During the first 16 weeks of treatment, summaries will be provided for the following treatment groups:

- BMS-986165 6 mg QD
- Apremilast
- Placebo

During the first 24 weeks of treatment, summaries will be provided for the following treatment groups:

- BMS-986165 6 mg QD (subjects continuously taking BMS-986165 6 mg QD)
- Apremilast

Summaries will be provided for subjects who have continuous treatment throughout the entire study with either BMS-986165 or apremilast using the following treatment groups:

- BMS-986165 6 mg QD
- Apremilast

Summaries of all subjects exposed to BMS-986165 6 mg QD will also be provided as applicable. Adverse events will be summarized using exposure-adjusted incidence rates (EAIR) for these summaries.

Please note that there will be no Chinese subjects in the apremilast group due to lack of market approval of the agent in China.

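### SAP 6.2.3 stops the worst-grade and grade-shift laboratory tables at Week 16 while SAP 4.2 sets no cut-off, and no window is stated for counting CK grade 2 or higher

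*SAP*

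**What the plan says.** **Laboratory grades.** SAP 6.2.3 specifies two tables that give one worst result per subject: "Maximum postbaseline CTCAE grade for each applicable laboratory parameter through Week 16" and "Shifts from baseline based on maximum postbaseline CTCAE grade through Week 16". Its other content, absolute values and changes by time point plus DILI and Hy's Law summaries, carries no Week 16 limit. SAP 4.2, which defines the safety outcomes, has laboratory abnormalities "presented as the worst postbaseline toxicity group" and also lists "Shifts from baseline to maximum postbaseline value". Neither has a time limit there.

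**Groups after Week 16.** SAP 6.0 plans summaries for subjects continuously treated with BMS-986165 or apremilast over the whole study, and adds: "Summaries of all subjects exposed to BMS-986165 6 mg QD will also be provided as applicable". Protocol 9.5 lists safety groups after Week 16, among them an all-BMS-986165 group that "includes subjects on placebo that switched to BMS-986165 6 mg QD". Protocol 9.5.3 plans an incidence summary of out-of-range values with no time limit, though it does not mention CTCAE grades. SAP 2.5 does not list a Week 16 restriction among its important changes from the protocol.

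**CK.** SAP 4.2 names CK elevation of grade 2 or higher as a treatment-emergent event of interest, and treatment-emergent there runs to 30 days after the final dose or to a later last visit. SAP 6.2.1.1 leaves CK out of its preferred-term list and says that it "will be summarized as CTCAE grade 2 or higher in the clinical laboratory summaries". It gives no window.

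**eC-SSRS.** SAP 6.2.6.2 ends the shift and worst-value tables at Week 16, while SAP 4.2 does not. Item responses are still summarized by time point.

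**The concern.** The outcome section and the analysis section of the SAP describe the same quantities over different periods. A programmer who follows 6.2.3 produces worst-grade and shift tables for the first 16 weeks only. A programmer who follows 4.2 produces them for the whole study.

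The difference matters because most planned BMS-986165 exposure comes after Week 16, and placebo and apremilast switchers have none before it. A table of means by visit does not answer how many subjects ever reached grade 3 on a given parameter; that needs one worst grade per subject.

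CK is the sharpest case. It is a named event of interest, and the count of subjects at grade 2 or higher depends directly on whether the window is 16 weeks or the whole treatment-emergent period. The SAP does not say which.

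**Working it through.** The plan states no figure to reproduce. The check compares the texts and then sizes the difference.

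**Passages side by side**
- Worst grade: 4.2 no cut-off; 6.2.3 Week 16.
- Shift: 4.2 no cut-off; 6.2.3 Week 16.
- CK grade 2 or higher: 4.2 treatment-emergent window; 6.2.1.1 none stated; the per-subject grade tables in 6.2.3 Week 16.
- For comparison, the marked-abnormality tables for vital signs (6.2.4) and ECGs (6.2.5) have no Week 16 limit.

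**Visits (protocol Tables 2 and 3)**
- Chemistry, which includes CK, and hematology after baseline: Weeks 1, 2, 4, 8, 12, 16 (6 visits), then 20, 24, 28, 32, 36, 40, 44, 48, 52 (9 visits). Outside the grade tables: 9/15 = 60%.
- eC-SSRS after baseline: Weeks 8 and 16, then 28, 40 and 52. Outside the shift and worst-value tables: 3/5.

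**Exposure.** Inputs: about 600 subjects at 2:1:1, so 300/150/150; placebo switches at Week 16; apremilast subjects without PASI 50 switch at Week 24; treatment lasts 52 weeks.
- Randomized BMS-986165 arm, no dropout: 300 × (52 − 16) = 10,800 of 300 × 52 = 15,600 subject-weeks, or 69.2%.
- Same arm, assumed linear dropout reaching a fraction d at Week 52. Mean weeks in total = 52(1 − d/2); mean weeks up to Week 16 = 16 − d × 16²/(2 × 52).
  - d = 10%: (49.40 − 15.75)/49.40 = 68.1%
  - d = 30%: (44.20 − 15.26)/44.20 = 65.5%
  - d = 50%: (39.00 − 14.77)/39.00 = 62.1%
- All BMS-986165 exposure, no dropout, no apremilast switching: (10,800 + 150 × 36)/(15,600 + 150 × 36) = 16,200/21,000 = 77.1%.
- If all 150 apremilast subjects switch, add 150 × 28 = 4,200 to both parts: 20,400/25,200 = 81.0%.
- With 50% linear dropout these two become 71.1% and 75.4%.
- Switchers alone: all of their BMS-986165 exposure falls after Week 16.

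Dropout and switching rates are assumptions; the documents do not give them. The shares measure planned exposure outside the two tables, not data lost.

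**The case against.** The case on the other side is substantial.

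- **A reader might infer that laboratory safety after Week 16 goes unreported.** The documents do not support that. By-visit values and changes, DILI and Hy's Law summaries, and the ALT or AST outcome above 5 times ULN carry no Week 16 limit. Abnormalities reported as adverse events enter the TEAE and exposure-adjusted tables. SAP 6.2.1.1 also summarizes additional information collected for some events, and protocol 8.2.1 allows such information for CK. This stands and narrows the point to the per-subject grade tables. It does not close the gap: under protocol 8.2.7 a laboratory result becomes an adverse event only if it is clinically significant, meets the SAE definition, or led to interruption, discontinuation or corrective treatment.
- **A reader might call the CK window a flat contradiction.** That is too strong. SAP 6.2.1.1 sends CK to the laboratory summaries but does not cite the Week 16 tables or adopt their limit. The window is unstated, and it is inconsistent with the treatment-emergent definition only if CK is taken from those tables.
- **SAP 6.0 and 6.2 promise summaries by period and for all exposed subjects.** They do, but as applicable and without naming a grade table. A general sentence does not override the explicit limit in 6.2.3.
- **Week 16 ends the placebo-controlled period.** This is a good reason to have Week 16 tables. It does not explain why 4.2 differs, or why no later table is specified.
- **The tables may sit in the data presentation plan** mentioned in the SAP document history. They may. That plan is not among the documents, so the finding concerns only what the SAP specifies.
- **Consequences are limited.** Alpha, power and the coprimary analyses are untouched, investigators review every laboratory report, the DMC reviews laboratory data, and descriptive tables can be added later. All of this stands and limits the severity.

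**Conclusion.** The point holds as an internal inconsistency with a practical consequence. The Week 16 limit in 6.2.3 is a stated rule, not a missing detail. Following it leaves most planned BMS-986165 exposure outside any specified worst-grade table: 69% in the randomized arm without dropout (62% at an assumed 50% dropout), and about 71% to 81% of all BMS-986165 exposure across the assumed dropout and switching ranges. These figures rest on the planned sample size, allocation and visit schedule.

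For CK, the conclusion is that the window is unclear and needs to be stated. The eC-SSRS mismatch is real but minor: by-visit counts continue, adjudicated events are summarized under protocol 9.5.1, and protocol 9.5.4 asks only for summaries where applicable. The inconsistency is worth correcting; it does not threaten the trial's efficacy conclusions.

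**What to change.** 1. Keep the Week 0 to 16 tables for the placebo-controlled comparison.
2. In SAP 6.2.3, add maximum-grade and grade-shift tables through Week 52 for subjects continuously on BMS-986165 or apremilast, and for all BMS-986165-exposed subjects.
3. State the baseline for switchers, for example the last value before the first BMS-986165 dose. SAP 8.1 uses the randomization value, with a screening value as fallback, unless otherwise stated, so a specific rule can be added without conflict.
4. In SAP 6.2.1.1, state that CK grade 2 or higher is counted over the treatment-emergent window of SAP 4.2. An exposure-adjusted CK rate is optional. It would be a new analysis and would need an onset rule, such as the first laboratory date at grade 2 or higher, because the rate in SAP 8.1 is built on adverse event onset dates.
5. Give the eC-SSRS shift and worst-value summaries the same window in SAP 4.2 and 6.2.6.2.
6. If the data presentation plan already holds these tables, name them in the SAP.

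The cost is a few extra tables on data already collected and a derivation rule for switchers, with no change to study conduct. The limitation is that the later results have no concurrent placebo control and should be labelled accordingly.

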## 6.2.4 Vital Signs and Physical Findings

Vital signs, including weight, will be summarized by time point, as applicable. The following summaries will be provided for each parameter:

- Absolute and change from baseline values
- Number and percentage of subjects for the following:
  - Marked abnormality for each abnormality category as defined in [Section 4.2](#)

## 6.2.5 ECGs

ECG parameters will be summarized by time point, as applicable. The following summaries will be provided for each parameter:

- Absolute and change from baseline values
- Number and percentage of subjects for the following:
  - Marked abnormality for each abnormality category as defined in Section 4.2

## 6.2.6 Other Safety Data

### 6.2.6.1 PHQ-8

PHQ-8 total score will be summarized by time point, as applicable. The following summaries will be provided:

- Absolute and change from baseline values
- Number and percentage of subjects:
  - Shifts from none, mild, moderate, moderately severe and severe scores at baseline and at each time point

### 6.2.6.2 eC-SSRS

Suicidal ideation and behavior individual item responses will be summarized by time point, as applicable. The following summaries will be provided:

- Number and percentage of subjects with positive responses on suicidal ideation and/or suicidal behavior questions for each question and overall all questions within suicidal ideation and suicidal behavior
- Shifts from baseline based on maximum postbaseline response through Week 16
- Worst postbaseline value for suicidal ideation and behavior through Week 16

## 6.3 General Methodology

The following standards/ methods will be used:

- Statistical package(s) planned to be used
  - All analyses will use SAS version 9.4 or higher.
- Standard summary statistics for continuous and categorical variables:

Sponsor: Bristol-Myers Squibb

Protocol no: IM011046

- Unless otherwise noted, categorical variables will be summarized using counts and percentages. Percentages will be rounded to one decimal place, except 100% will be displayed without any decimal places and percentages will not be displayed for zero counts.
- Continuous variables will be summarized using the number of observations (n), mean, standard deviation (SD), median, minimum and maximum. The median, minimum and maximum values will be displayed to the same level of precision as the raw data, the mean to a further decimal place and the SD to two additional decimal places.
- Variables will be summarized by period, treatment group, and time point, as applicable.

### 6.3.1 Subject Populations and Disposition

The number of subjects enrolled/screened and the number and percentage of subjects randomized, treated, and in each analysis population will be presented. The number and percentage of subjects randomized in each region, country, and site will be presented.

Additionally, the following summaries will be provided for the FAS by treatment group and overall:

- Number and percentage of subjects who completed 16 weeks of treatment
- Number and percentage of subjects who discontinued treatment prior to Week 16 and reason for treatment discontinuation
- Number and percentage of subject who completed 24 weeks of treatment, who discontinued treatment prior to Week 24 and post Week 16, and those who discontinued at any time prior to week 24 and reason for treatment discontinuation. Denominator will be the number of subjects in the FAS.
- Number and percentages of subjects who completed 52 weeks of treatment, who discontinued treatment prior to Week 52 and post Week 24, and who discontinued treatment at any time and reason for treatment discontinuation. Denominator will be the number of subjects in the FAS.

### 6.3.2 Demographic and Baseline Characteristics

Demographic and baseline characteristics will be summarized by treatment group for the FAS. Demographic characteristics include the following:

- Sex
- Race
- Ethnicity
- Age (in years, at time of signing informed consent) and age category (<65 vs ≥65)
- Weight (in kg, at baseline) and weight category (≥90 kg, <90 kg)
- Body mass index (BMI in kg/m^2, at baseline)
- Geographic region (U.S., Japan, China, Rest of World)
- Prior biologic use for psoriasis, psoriatic arthritis and other inflammatory diseases only (yes, no)
- Reason for discontinuation of prior biologic use
- Prior systemic treatment use (yes/no)
- Prior phototherapy use (yes/no)
- Stratification factors obtained from IRT: geographic region by prior biologic use and by body weight
- Stratification factors obtained from database: geographic region by prior biologic use and by body weight
- sPGA (3, 4)
- PASI score (≤20, >20)
- BSA involvement (10-20, >20)
- Duration of disease (< 10 y, ≥ 10 y)
- Age at disease onset (<18, 18-39, ≥40)

Sponsor: Bristol-Myers Squibb

Protocol no: IM011046

Additional demographics or baseline data may be added to summary tables.

General medical history and medical history related to psoriasis will be coded using the Medical Dictionary for Regulatory Activities (MedDRA). General medical history data will be summarized for each SOC and PT by treatment group and overall for the FAS. Separate tables will be provided for psoriasis medical history.

### 6.3.3 Prior and Concomitant Medications

Prior and concomitant medications will be coded according to World Health Organization-Drug Dictionary WHO-DD (version at the time of DBL) and will be summarized by Anatomic Therapeutic Classification (ATC) and preferred term (PT) by treatment group for the As-treated population. The number and percentage of subjects using at least one medication and each medication will be displayed by treatment group. Subjects taking more than one medication within the same ATC or PT will be counted once.

Summaries will be provided for prior medications and medications that started prior to first treatment and were ongoing after first treatment start date as well concomitant medications.

Medication dates will be imputed according to algorithms detailed in [Section 8.0](#). The imputed dates will be used to assess whether medications should be included in the summaries as prior or concomitant, however the original, partial dates will be included in data listings.

#### 6.3.3.1 Psoriasis, Psoriatic Arthritis and Other Inflammatory Disease Related Systemic Medications

Prior medications and medications that started prior to first treatment and were ongoing after first treatment start date for systemic biologic and non-biologic medications will be summarized as described above for the number and percentage of subjects using each reported medication.

#### 6.3.3.2 Concomitant High Potency Corticosteroid Use

The number and percentage of subjects using at least one high potency topical corticosteroid at Week 24 will be summarized by treatment group. Additionally, corticosteroids will be summarized by ATC and PT.

### 6.3.4 Exposure

#### 6.3.4.1 Duration of Treatment

##### Duration by Group

Overall duration of each treatment, in days, will be calculated for each subject in each treatment group. Subjects are dispensed study treatment at each visit, starting with Day 1 (Week 0) and at each subsequent visit. The date of first dose of study treatment is the Week 0 [redacted] dosing date and is recorded on the eCRF. If this date is missing, then the earliest drug dispensation date will be used. The last dose date is recorded on the end of treatment page in the eCRF. If this date is missing, then the latest date from the [redacted] page or drug accountability return date will be used.

Duration of treatment will be summarized descriptively by randomized treatment group.

##### BMS-986165:

Subjects randomized to BMS-986165 will have their duration of treatment derived as:

- Date of last dose – date of first dose +1

##### Placebo:

For subjects randomized to placebo, duration is defined as:

- Placebo = Date of last dose of placebo – date of first dose +1
- BMS-986165 = Date of last dose of BMS-986165 – date of first dose of BMS-986165 +1

### **Apremilast:**

For subjects randomized to apremilast, the Week 24 date will be used as the date of last dose of apremilast and the date of first dose of either apremilast or BMS-986165 for the subsequent period. Subjects who receive apremilast at Week 24 through to Week 52 will be counted as a sum of the first 24 weeks of treatment and the next treatment period.

- Apremilast (Wk 0 through Wk 24) = Week 24 date – date of first dose +1
- Apremilast (Wk 24 through Wk 52) = Date of last dose – Week 24 date
- Total Apremilast = Duration of apremilast Wk 0-24 + duration of apremilast Wk 24-52
- BMS-986165 = Date of last dose of BMS-986165 – Week 24 date

Total apremilast duration of treatment will be displayed as well as BMS-986165 treatment duration. If subject discontinues their study treatment during the initial 24 weeks of apremilast treatment, the date of last dose will be used as the duration of apremilast.

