## 6.6 Statistical Impacts Due to COVID-19

### 6.6.1 Impact on Efficacy Endpoints

There are no COVID-19-related impacts to the Week 16 and Week 24 endpoints as all subjects remaining in the trial completed these visits prior to COVID-19 restrictions. Key secondary efficacy endpoints involving later visits may be impacted by COVID-19 in the form of missing data and/or a treatment assignment defaulting to BMS-986165. If a subject has missing data or is switched to BMS-986165 from a different treatment due to COVID-19 during the Week 24 through Week 52 period, the subject will be excluded from the analysis.

Key secondary efficacy endpoints that may be impacted include the following:

- sPGA 0/1 response at Week 52 and at Week 24
- PASI 75 response at Week 52 and at Week 24
- PASI 90 response at Week 52 and at Week 24

A sensitivity analysis will also be performed for the above endpoints using the last observed value. The data handling rules to be used are as follows for subjects with missing data or for those subjects who switch to BMS-986165 from a different treatment due to COVID-19:

- If the subject is missing the Week 52 response value (ie, sPGA 0/1, PASI 75, PASI 90), then the last observed response value during the Week 24 through Week 52 period will be carried forward to the Week 52 value
- If the subject is switched to BMS-986165 from a different treatment due to COVID-19, then the last observed response value prior to the switch will be carried forward to the Week 52 value

Censoring rules will be applied to the time to first loss endpoints evaluated for the maintenance of efficacy of BMS-986165 through Week 52 in subjects who were originally randomized to BMS-986165 and impacted by COVID-19-related issues post Week 24:

- Subject has missing visits (ie, efficacy assessments not performed) after Week 24 and assuming loss of response was not observed prior to missing visits:

Sponsor: Bristol-Myers Squibb  
Protocol no: IM011046

- If the subject returns at a later visit and is found to have had a loss of response, midpoint imputation will be used to determine time to first loss (ie, midpoint of the censoring interval).
- If the subject returns at a later visit and has not had a loss of response, then the subject will continue to be evaluated for time to first loss.
- If the subject is discontinued from the study treatment, then the subject will be censored at the time of study treatment discontinuation.

Time to first loss endpoints include:

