## 6.6.2 Impact on Safety Endpoints

No modifications will be made for the analysis of safety data due to COVID-19-related issues. There will not be any additional safety data handling considerations for missing data or treatment interruptions due to COVID-19.

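### The apremilast exposure rule starts BMS-986165 duration at Week 24, so it overstates that duration for any subject switched later because of COVID-19

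*SAP*

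**What the plan says.** SAP 6.3.4.1 gives separate duration rules by randomized arm. For the apremilast arm, "the Week 24 date will be used as the date of last dose of apremilast", and the next segment, on either drug, starts from the same date. Two post-Week-24 formulas follow:

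- "Apremilast (Wk 24 through Wk 52) = Date of last dose – Week 24 date"
- "BMS-986165 = Date of last dose of BMS-986165 – Week 24 date"

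For the placebo arm, the same section counts time on BMS-986165 from its own first dose, subtracting the "date of first dose of BMS-986165 +1".

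SAP 6.6.1, on COVID-19, says that later efficacy endpoints may be affected by "missing data and/or a treatment assignment defaulting to BMS-986165". A subject who "is switched to BMS-986165 from a different treatment due to COVID-19 during the Week 24 through Week 52 period" is excluded from the Week 52 efficacy analysis, with a carry-forward sensitivity analysis. SAP 6.6.2 then states: "No modifications will be made for the analysis of safety data due to COVID-19-related issues".

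SAP 8.1 defines EAIR time at risk by the start and stop dates of the particular treatment and counts events that occur while on it. It gives no start date for a treatment begun partway through Period 3. SAP 6.0 makes EAIR the adverse event summary for all subjects exposed to BMS-986165.

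**The concern.** The apremilast rule recognises two paths after Week 24: stay on apremilast, or start BMS-986165 at Week 24. SAP 6.6.1 provides for a third: pass Week 24 on apremilast and move to BMS-986165 later. The efficacy section handles that path and the exposure section does not.

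For a subject on the third path, the BMS-986165 formula counts weeks on apremilast as weeks on BMS-986165. The displayed duration is then wrong. Because the EAIR definition leaves the start date open for a switch within a period, two programmers could also derive different person-time, and place events differently, from the same text.

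**Working it through.** The documents state no exposure figure for these subjects, so there is nothing to reproduce. The check applies the SAP formulas to one illustrative subject and compares the result with actual days.

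**Why the switch must be from apremilast and after Week 24.** Placebo subjects have already moved to BMS-986165 at Week 16 (SAP 2.3). SAP 6.6.1 says all remaining subjects completed Week 24 before COVID-19 restrictions, and its sensitivity analysis carries forward the last response before the switch.

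**Inputs.** Nominal days from protocol Tables 2 and 3: Week 16 = 113, Week 24 = 169, Week 28 = 197, Week 36 = 253, Week 44 = 309, Week 48 = 337, Week 52 = 365. Assumptions: first dose on Day 1, last dose on Day 365, no dosing gap, first BMS-986165 dose on the switch day.

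**The rule works for the two intended paths.** The first segment is 169 − 1 + 1 = 169 days and the second is 365 − 169 = 196 days. They sum to 365.

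**A later switch on day s.** SAP 6.3.4.1 gives 365 − 169 = 196 BMS-986165 days for every s. Actual days are 365 − s + 1.

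| Switch visit | s | SAP days | Actual days | Excess |
|---|---|---|---|---|
| Week 28 | 197 | 196 | 169 | 27 |
| Week 36 | 253 | 196 | 113 | 83 |
| Week 44 | 309 | 196 | 57 | 139 |
| Week 48 | 337 | 196 | 29 | 167 |

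**The apremilast side, Week 36 switch.** Actual apremilast days are 252. The post-Week-24 apremilast formula does not say which drug's last dose it uses, so three readings are possible:

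1. Apremilast closed at Week 24: 169 + 196 = 365 days in total, with 83 apremilast days moved to BMS-986165.
2. Last apremilast dose (Day 252): apremilast = 169 + (252 − 169) = 252. The total is 252 + 196 = 448, with 83 days counted twice.
3. Last study dose (Day 365): apremilast = 169 + 196 = 365. The total is 365 + 196 = 561, with all 196 days after Week 24 counted twice.

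Readings 2 and 3 give totals that are impossible for a subject treated for 365 days.

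**Aggregate size, under assumptions.** With 600 subjects randomized 2:1:1 the arms are 300, 150 and 150. With no dropout, BMS-986165 exposure from its own arm and the placebo switchers is (300 × 365 + 150 × 253)/365.25 = 403.7 person-years, where 253 = 365 − 113 + 1.

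- Assuming 3 to 20 subjects with an excess of 83 days each: 3 × 83/365.25 = 0.68 and 20 × 83/365.25 = 4.54 person-years, or 0.2% to 1.1% of 403.7.
- Assuming 10 subjects with an excess of 83 to 139 days: 2.3 to 3.8 person-years. If 30% to 70% of the apremilast arm continues on apremilast after Week 24, total BMS-986165 exposure is 460.0 to 427.8 person-years and apremilast exposure is 93.6 to 125.7. The shares are 0.5% to 0.9% of BMS-986165 and 1.8% to 4.1% of apremilast.
- Assuming 1 to 40 subjects over the same ranges: 0.2 to 15.2 person-years, or 0.05% to 3.6% of BMS-986165 and 0.2% to 16% of apremilast.

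The apremilast shares measure a loss of apremilast time only under reading 1.

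**The case against.** The strongest reply is that this is a definitional gap in a descriptive summary. SAP 6.3.4.1 is summarized by randomized group, and nothing links its dates to the EAIR. SAP 8.1 uses treatment-specific dates and counts events while on that treatment. SAP 5.0 analyses the As-treated population by treatment received. On those words, an event at Week 30 on apremilast is an apremilast event. No primary or key secondary test is touched.

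Most of that stands, and it rules out three stronger readings that a reader might infer:

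- **That subjects were in fact moved.** SAP 6.6.1 is conditional and gives no count.
- **That apremilast events are assigned to BMS-986165.** No section says so. It would happen only if the Week 24 date, or the Period 3 first dispensing date in SAP 8.1, were taken as the BMS-986165 start. For these subjects both precede the first BMS-986165 tablet.
- **That SAP 6.6.2 forbids a correction.** It bars COVID-specific handling. Using the actual start date of a treatment is not COVID-specific.

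The reply does not rescue the duration formula. "Date of last dose of BMS-986165 – Week 24 date" is an explicit rule, and following it gives a wrong number for any subject who switches after Week 24. Nor does SAP 8.1 say which start date applies to a switch within Period 3. SAP 6.2.1 allocates events to a period by first dispensing date, which does not separate two drugs taken within one period.

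**Conclusion.** The concern holds as a duration error plus an open definition. For any subject switched from apremilast to BMS-986165 after Week 24, the SAP formula overstates BMS-986165 duration by 27 to 167 days across switches at Week 28 to Week 48. It also leaves unclear whether those weeks are removed from apremilast or counted twice. Misassignment in the EAIR is possible but is not prescribed.

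The aggregate effect on BMS-986165 exposure is probably small: about 0.2% to 1.1% with an assumed 3 to 20 subjects switched at Week 36. It could be proportionally larger for apremilast, whose exposure base is smaller. These figures rest on planned arm sizes, no dropout and assumed numbers of switched subjects. The true number is not in the documents and may be zero. The correction is worth making because the rule as written is wrong for these subjects and is easily put right.

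**What to change.** In SAP 6.3.4.1 and 8.1, add a rule for any subject randomized to apremilast who starts BMS-986165 after Week 24:

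- End apremilast at the actual last apremilast dose. Ending it the day before BMS-986165 was dispensed would count any dosing gap as apremilast exposure.
- Start BMS-986165 at its actual first dose or, if that date is missing, at the first BMS-986165 dispensing date in the IRT. This follows the form already used for placebo switchers.
- State which drug's last dose the post-Week-24 apremilast formula uses.
- State that duration, EAIR and adverse event attribution all use these dates, and add to SAP 6.6.2 that this includes COVID-19 switches.

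The cost is a few sentences of SAP text and the matching programming. The IRT assigns a kit number at each dispensing (SAP 2.3), so no new data collection is needed, and no treatment rule changes.
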